The study will involve three groups of participants: 1) Clinicians; 2) Agency Leaders; and 3) Youth. Clinician Inclusion Criteria: (1) Clinician will be at least a part-time employee providing psychosocial treatment at the study agencies. (2) Clinician may conduct sessions in English or Spanish, but must be able to speak, read and understand English well enough to participate in English-language interviews, trainings, and consultation calls. Agency Leader Inclusion Criteria: (1) Agency leaders will be individuals in leadership positions (e.g., CEO, clinical director) at the study agencies. (2) Must be able to speak, read and understand English well enough to participate in English-language interviews. Youth Inclusion Criteria: (1) Male or female youth between the ages of 11-17 years receiving mental health services in the outpatient, intensive outpatient, and/or intensive home-based services at the participating clinics; the research subsample will be restricted to ages 11-16 to avoid having to re-consent individuals who turn 18 during the study. (2) If the family consents to complete additional research measures, one parent and/or primary caregiver must be available and willing to participate in all study assessments. (3) Adolescent and at least one parent/guardian are able to complete all study procedures in English or Spanish. For the Aim 1 pre-pilot, the adolescent and guardian must be able to complete all study procedures in English; this decision was made so that study materials could be finalized prior to translating them into Spanish.

6) Number of Subjects*

Up to 15 agency leaders, up to 200 clinicians, and up to 2000 youth will take part in the study.

7) Study-Wide Recruitment Methods*

Recruitment and Referral Sources. Participants will be drawn from up to four clinic locations in Tennessee of Health Connect America, Inc. (HCA).

Youth and their caregivers (N = up to 20 dyads) will be included in the small pilot that is part of Aim 1. Clinicians taking part in this pilot study will be asked to try out the measurement-base care (MBC) system with clients on their existing caseloads. The research team will provide

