Youth and their caregivers will be included in Aims 2 and 3 in three ways. First, the four study clinics will be using the measurement-based care system with all clients receiving in outpatient and intensive outpatient mental health services (up to 2000 youth falling in the target age range) and have agreed to incorporate the study randomization scheme as a quality improvement effort. PI [name] has successfully used this approach in two previous randomized controlled trials of MBC^{46,47}. Second, in the session where the youth and caregivers complete the MBC measures through the Mirah platform, they will be recruited via the Mirah Platform to complete additional measures using the same procedures described for the Study 1 pilot trial. Recruitment will take the form of presenting a recruitment screen, followed by the consent form if they indicate they are interested in learning more about the study at the end of their measures; families will also be notified that this will be happening via a flyer that the clinic will be using to tell them about the Mirah system. These flyers are tailored for each office, but we have uploaded one as an example (Mirah PACE flyer- Nashville). We have also uploaded a copy of the recruitment screen (Recruitment Information for Research Subsample). The clinics may use Mirah at the clinic intake session, before the decision has been made which services the youth will receive. If a family consents to be in the research sample and then the youth does not go on to be assigned to one on the services using Mirah, they will be contacted and informed that they will no longer be eligible to take part in the study. Up to 400 youth and their caregivers will be enrolled in these additional research activities. Finally, for the final phase of the mixed-method study of implementation factors, a subset of up to 12 families who agreed to take part in the research study, stratified by their level of adherence to the MBC system, will be recruited with the assistance of their clinicians, who will provide them with a flyer describing the study (uploaded as PACE Family Triad Interview Recruitment Flyer) and asked if they would be interested in being contacted by research staff to hear about an opportunity to participate in qualitative interviews to better understand their experiences using the system. Families will be paid up to \$60 in gift cards (\$30 per informant) for participating in those interviews.

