dataset for individuals who consent to take part in the research subsample. We have uploaded a variable list of the variables we will be requesting from Mirah. After the first time a youth and their caregiver complete the MBC measures, the Mirah system will proceed to screens with recruitment and consent information for participation in the Research Subsample. Youth and caregivers will be asked to assent/consent to complete additional research measures. Each time they complete Mirah measures for routine sessions, youth and caregivers will be administered one additional mechanism item; this item will be included in up to 12 sessions after they enroll in the study. In addition, they will complete a longer set of research measures will including the Ohio Scales and additional mechanism measures; these will be administered at study enrollment, 6 weeks later, and 12 weeks after study enrollment. These longer sets of research measures will be administered via the REDCap system, with links e-mailed directly to the family by research staff. Additional Research Subsample Measures have been uploaded under Study Documents. Families who consent to be a part of this Research Subsample will be paid up to \$30 for completing these measures (the project will e-mail them a \$10 gift card per major assessment completed either directly through e-mail or by using Qualtrics and Tango Card). Clinicians treating clients in the Research Subsample will also be asked to complete additional measures for those clients and will be paid \$36 for completing those measures. The Mirah system does not have a way to only recruit clients whose clinicians have consented to be in the research study or to tailor the measure schedule for those clients. Therefore, if a client agrees to be in the study and their clinician has not, the study will contact the clinician, let them know that they will be receiving links to research measures, and see whether they would like to consent to be in the study at that point. If they do not, then they will be instructed to disregard the requests for them to complete measures. These measures are also included in the Research Subsample Measures upload under Study Documents.

METHODS FOR AIM 3. MIXED-METHODS ANALYSIS OF IMPLEMENTATION FACTORS

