This study only presents minimal risks to participants.

14) Withdrawal of Subjects*

Participants and their parents/guardians may be withdrawn from the study without their consent if they are withdrawn from clinical care in the participating clinics. Should the client be terminated or transferred in accordance with the local clinic policy, he/she will be withdrawn from the study. In addition, participants may be withdrawn for the following reasons:

- The participant is no longer able to attend clinic visits or complete research assessments.
- There may be other reasons that are unforeseen at this time.

Those participants who voluntarily withdraw from treatment may be asked to complete the 6 and 12 week assessments for data collection purposes, if appropriate.

Clinicians may be excluded from the study for any of the following reasons:

- They leave the clinic and are no longer seeing clients at the agency.
- They are unable to attend and/or participate in training and consultation meetings.
- They are determined inappropriate for the research study (i.e. failure to adhere to treatment, failure to adhere to study procedures).

15) Risks to Subjects*

This study is considered to involve minimal risk for all participants. For the clinician and agency leader participants, participants, the main risk is that they will be asked information about their work in a group interview setting where their colleagues might hear their answers. In addition, the clinicians taking part in the pre-pilot and RCT may experience slight discomfort participating in MBC consultation calls or from seeing client progress reports. However, clinicians could experience this same discomfort in the routine supervision they receive. For youth and caregiver participants, there could be some risk of discomfort from disclosing information through the Mirah platform, although this discomfort is not anticipated to exceed that involved in typical

clinical procedures. In addition, they may experience minor discomfort giving feedback about their experiences using the MBC system.

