Clients and Caregivers in the Research Subsample. At least 420 clients and caregivers will complete additional research measures via the Mirah system during the Aim 1c pre-pilot and the Aim 2 trial. Consent procedures will differ slightly for the two phases of the study. For the pre-pilot, caregivers will view a consent form and youth an assent form the first time they complete these measures in the Mirah system. If they have questions before participating, they will have the option to provide a phone number and ask for a call from study staff before deciding. For the Aim 2 Research Subsample, which involves a much larger sample of youth being recruited when they start treatment, youth and caregivers will view recruitment information when they complete their clinic intake questionnaires via Mirah. If they click that they are interested in the study, they will proceed to a screen with the consent/assent document. After reading the document, they will indicate yes, no, or "I have questions." If they have questions, they will next proceed to a Frequently Asked Questions (Research Subsample Frequently Asked Questions Page, uploaded in consent materials) page to see if their question is there. If not, they will be provided with the project phone number to call to ask questions. If they indicate at the intake that they have questions and do not consent, the study recruitment and consent/assent information will be presented one more time prior to their completion of the Mirah measures for their first session. If they do not agree to be in the study at that point, they will no longer be eligible to be part of the research subsample. Because youth and caregivers receive different links to complete their Mirah questionnaires, they will be asked to assent and consent separately, and it is possible that youth may consent prior to their caregivers consenting. However, neither youth nor caregivers will complete research measures unless both have consented/assented. We are requesting a waiver of signed consent for both the pre-pilot and research subsample subsample participants. For the pre-pilot obtaining written consent would increase the study risk by providing identifying information to the study team. For the research subsample, the research

team will obtain identifying information from participants in order to give them gift cards, but the study is online, so it is not feasible to get signed consent and the study is minimal risk.

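### Section 14 has conflicting withdrawal rules, one of which can end week-6 and week-12 Ohio follow-up for terminated or transferred Research Subsample youth, and Aim 2b names no exit reasons

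*Combined protocol and SAP*

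**What the plan says.** Section 14 (Withdrawal of Subjects) contains four rules that bear on a youth who leaves clinic care:

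- Withdrawn from clinical care, discretionary: "Participants and their parents/guardians may be withdrawn from the study without their consent if they are withdrawn from clinical care in the participating clinics".
- Terminated or transferred, mandatory: "Should the client be terminated or transferred in accordance with the local clinic policy, he/she will be withdrawn from the study".
- Unable to attend clinic visits or to complete research assessments: listed among the reasons for which a participant may be withdrawn.
- Voluntary leavers, with follow-up allowed where appropriate: "Those participants who voluntarily withdraw from treatment may be asked to complete the 6 and 12 week assessments for data collection purposes".

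Section 9 makes the youth- and caregiver-reported Ohio scale a primary endpoint, in the Research Subsample only. Section 10 says of the longer research measures, which include it, that "these will be administered at study enrollment, 6 weeks later, and 12 weeks after study enrollment". On delivery it says: "These longer sets of research measures will be administered via the REDCap system, with links e-mailed directly to the family by research staff". Section 30 adds that the research "team will obtain identifying information from participants in order to give them gift cards".

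Section 7 deals separately with families who consent at intake but whose youth is never assigned to a service using Mirah: "they will be contacted and informed that they will no longer be eligible to take part in the study".

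In Section 12, Aim 2b models attrition and completion of all 12 weeks against condition, client and clinician factors, to inform the next trial's design and its projected attrition. The text neither defines attrition nor names reasons for exit.

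**The concern.** Staff cannot apply Section 14 consistently. A planned discharge, a move to another clinician or program, or a family that stops attending and is then closed under clinic policy could each fall under more than one rule. Some of those rules leave follow-up open and one ends study participation.

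Clients are randomized when the clinic adds them to Mirah, so these exits come after randomization. If the mandatory rule is applied, week-6 and week-12 Ohio and mechanism scores may be lost because of protocol wording, not because the family stopped responding.

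The second stake is Aim 2b. If its attrition count mixes imposed withdrawal, leaving care, withdrawal of consent and non-response, the planners of the next trial cannot tell which losses a new design would share. That matters however much power is lost here.

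**Working it through.** **1. Does collection depend on the clinic?**

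Section 10 times the longer measures from study enrollment and has research staff e-mail the links, so no clinic visit is needed. Section 5 requires youth to be "receiving mental health services in the outpatient, intensive outpatient, and/or intensive home-based services at the participating clinics", but as an entry criterion. Section 14 itself contemplates assessments after voluntary leaving.

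Some text points the other way. The clinic-visit bullet in Section 14 ties participation partly to attendance. Section 30 says the subsample completes its additional measures through Mirah. Sections 15 and 27 say no identifying information is collected from youth, which does not fit e-mailed links or gift cards. Section 10 is the specific procedure and is taken to govern, but these statements need reconciling with it.

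**2. The plan's power figure**

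Section 12 gives power of .62 for the Research Subsample at d = .25, with 400 adolescents, at least 22 clinicians, 8% of variance at clinician level and p = .05 (two-sided assumed). The stated inputs alone do not reproduce it:

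| Model | Power |
|---|---|
| Simple two-sample, 200 per arm | .705 |
| Randomized within 22 clinicians, no effect variance between clinicians | .664 |
| Same, with 8% of variance removed by clinician | .701 |
| Same, plus an unstated effect-size variance of .041 | .621 |

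The steps below scale from the plan's own .62.

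**3. Scaling**

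Noncentrality at full information = 1.960 + z(.62) = 2.265.
Power at information fraction f = Phi(2.265 × sqrt(f) − 1.960).

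The documents give no exit rate, so exit of 10% or 25% of the 400 is an assumption, as is 25% to 50% response after exit.

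**4. Bounding case: exited families contribute nothing**

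f = 1 − loss × (1 − response).

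| Loss | 0% response | 25% response | 50% response |
|---|---|---|---|
| 10% | f = .900, power .575 | f = .925, power .587 | f = .950, power .598 |
| 25% | f = .750, power .501 | f = .8125, power .533 | f = .875, power .563 |

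**5. Planned case: the multilevel model keeps earlier waves**

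A three-wave generalized least squares calculation gives the information retained for the arm difference in change. It uses assumed correlations r(0,6)/r(6,12)/r(0,12) of .5/.5/.5, .6/.6/.4 and .7/.7/.5, with exit before or after week 6. The retained fraction f0 is about .92 to .95 at 10% loss and .80 to .87 at 25% loss.

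With response r after exit, approximately f = f0 + r × (1 − f0).

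| Loss | f0 | Power, no follow-up | Power, r = 25% | Power, r = 50% | Gain |
|---|---|---|---|---|---|
| 10% | .92 | .584 | .593 | .602 | .009 to .018 |
| 10% | .95 | .598 | .604 | .609 | .006 to .011 |
| 25% | .80 | .526 | .551 | .575 | .025 to .049 |
| 25% | .87 | .561 | .576 | .591 | .015 to .030 |

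The gain is therefore about .006 to .018 at 10% loss and .015 to .049 at 25%. With no response after exit it is zero.

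**The case against.** The strongest reply is that the harm is possible but not shown. Section 14 never says that data collection is forbidden after termination, and the sentence just before the mandatory one is permissive. The clinic-visit bullet suggests that the authors did see participation as linked to attendance. The planned multilevel model uses the waves already collected, and the analysis of variance that would usually drop incomplete cases is only a fallback for a subsample that proves too small. Exit reasons may already be in the electronic health record that Aim 2b draws on, or in the separately uploaded Mirah variable list, which cannot be seen here. Consent may not cover contact after exit.

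Most of this stands, and it limits the point to a possible loss of unknown frequency and modest effect on power. It does not remove the inconsistency: follow-up is provided for voluntary leavers only, and the undefined terms leave one exit open to different rules.

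A reader might infer more than the documents support:

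- That the rule biases the arm comparison. Nothing shows that these exits relate to arm or outcome, and the multilevel estimate may be unbiased.
- That the session-based SFSS is safe, or that it is damaged. A transferred client might go on completing Mirah measures, and the documents do not say whether those scores would be used.
- That families whose youth never starts a Mirah service are wrongly excluded. Section 7 makes them ineligible, and that is not challenged.
- That exit reasons are not recorded anywhere. Only their absence from the Aim 2b text can be seen.

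**Conclusion.** The point holds as an inexpensive improvement. Section 14 is internally inconsistent and leaves its key terms undefined. For consented Research Subsample youth who started a Mirah service, its mandatory sentence can end collection of a primary endpoint that Section 10 allows to be collected without the clinic. Aim 2b, as written, may mix imposed withdrawal with non-response.

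The size cannot be established. On the assumed exit and response rates, follow-up after exit recovers at most about five points of power at d = .25 under the planned model, and often one or two. This rests on the plan's .62, on Section 10 prevailing over the conflicting statements, and on assumed wave correlations. The value for attrition planning does not depend on those power figures.

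**What to change.** 1. Reconcile the Section 14 sentences with one another, including the clinic-visit bullet, and define termination and transfer. Reconcile Sections 15, 27 and 30 with Section 10 on how the longer measures are delivered and what identifying information is held.
2. State that, for consented Research Subsample families, leaving clinic care does not by itself end research follow-up. Extend the existing 6- and 12-week request to terminated or transferred clients unless they withdraw consent, subject to consent and IRB coverage. Analyse them in the assigned arm.
3. State whether SFSS scores completed after a transfer are used.
4. Leave families never assigned to a Mirah service ineligible, and count them by arm.
5. Record the exit date and reason, or take them from the health record if already captured. In Aim 2b, report imposed withdrawal, leaving care, consent withdrawal and non-response separately by arm.

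The cost is protocol wording, a possible consent or IRB revision, reminder e-mails and perhaps one data field. Gift cards come to at most 2 × $10 = $20 per leaving family, within the existing $30: $800 for 40 families (10% of 400) or $2,000 for 100 (25%). Response after exit will probably be lower than among families still in care. None of this touches when or why the clinic ends care.
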